Expected Outcomes: For patients with circadian abnormalities, we predict more days of delirium. We expect this relationship will remain after controlling for age, gender, severity of illness and ventilator-free days. We expect that age, sedative-hypnotic medication dose and measures of sleep disruption will act as effect modifiers.

Aim 3: Evaluate the feasibility of providing daytime bright light in the ICU and examine the effect size of daytime bright light on circadian abnormalities in a pilot randomized controlled trial.

Rationale: Aim 3 will test our hypothesis that daytime bright light (hereafter bright light) is acceptable and tolerable to patients and has high fidelity and sustainability. Our approach to testing this hypothesis is a pilot RCT. We will randomize patients to usual care or to bright light daily while in the MICU. We will collect metrics of acceptability, tolerability, fidelity, and sustainability. The rationale for selecting bright light for this pilot intervention is that light is by far the dominant circadian entrainment cue.⁵¹ The proposed method delivers light to the patient and does not require the patient to have their eyes open or look directly into the light.⁵² In addition, brief light delivery early in the morning (e.g., 30 minutes of 10,000 lux directed at the patient), could cause undesirable circadian phase shifts in patient population who have circadian misalignment of the delayed type³⁰ It is our expectation that this intervention will be feasible to deliver in MICU patients. *We will use this Aim to calculate effect size for use in the anticipated large-scale circadian intervention to follow this pilot RCT.*

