Research Design: For Aim 3, we will screen and enroll 16 patients using the same inclusion/exclusion criteria as Aims 1 and 2. We will collect room light levels, circadian measurements, patient characteristics, and ICU care events as before. Patients will be randomized via simple randomization with assignment via random number generator to either usual care (n=5 patients) or to bright light for 4 hours daily (n=5 patients) or to bright light for 8 hours daily (n=5 patients). The bright light intervention will be delivered from 09:00 to 13:00 daily (4 hour group) or 09:00 to 17:00 daily (8 hour group). The bright light will be delivered from study day 2 until study day 5. The bright light will continue if the patient is transferred to the floor. Bright light will be delivered by a free-standing apparatus that delivers 10,000 lux at a temperature 5000K. The device will be placed at the bedside within 36 inches of the patient's head and is expected to provide at least 1,250 lux at the angle of gaze.

To remain in the study, the patient must be in the ICU through D2 (e.g., the first day of potential intervention and the night following). After D2, bright light and other study activities will continue if the patient is transferred out of the ICU to the general medical floor. To maintain as much control of the environment as possible, study patients will be booked only to private rooms on the general medical floor.

If symptoms of eye strain, visual disturbance or headache occur, patients will not continue bright light exposure. These reversible symptoms of direct bright light therapy are unlikely, but they will be tracked as a metric of feasibility under the category of patient tolerance. Feasibility Metrics will include patient acceptance (percent of patients/surrogates who agree to bright light when described to them); patient tolerance (percent of days that patients continue with additional treatments once exposed to bright light); intervention fidelity (percent of time per day that device delivers the planned dose of light); and intervention sustainability (percent of intended intervention days that device is used).

Expected Outcomes: We expect that bright light exposure is feasible, will decrease circadian misalignment, and will increase circadian amplitude.

STATISTICAL CONSIDERATIONS

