
Testing for Associations: Because both measures of circadian abnormality (misalignment and decreased amplitude) are continuous and normally distributed, multivariable linear regression models will test for associations, with light dose ratio serving as the exposure. Linearity of the associations will be examined graphically, and higher order terms will be considered as necessary. Models will be adjusted for age, gender, severity of illness, sepsis, risk of OSA, ICU care events per hour, and room temperature variables. We will test for modification of the association between light dose ratio and the outcomes by sepsis and risk of OSA. Because of the non-trivial intra-correlation coefficient expected from the serial correlation of the repeated outcome measures over time, models will employ generalized estimating equations with an auto-regressive correlation structure. Model fit will be evaluated with residual analysis, and significance will be defined as a two-sided p-value ≤ 0.05 . Power Calculations. For both continuous, normally distributed outcomes, power calculations assume a two-sided alpha of 0.05, power of 90%, a sample size of 100, and prevalence of covariates ranging from 20% to 50%. For minutes of misalignment, we further assume a mean of 180 minutes with a standard deviation of 95 and for amplitude a mean of 450 ng with standard deviation of 180.³⁰ Under these assumptions, our sample of 100 is sufficient to detect a range of minimal average shifts between 52-65 minutes of misalignment, and 98-123 ng of urinary aMT6 per

incremental change in the explanatory variables.

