Aim 3 Analytical Approach: Feasibility: Based on qualitative analysis, we will judge the intervention as feasible if it achieves at least 70% in each of the feasibility metrics: acceptance, tolerance, fidelity, and sustainability. Effect Size: Circadian abnormalities will be assessed as described under Aim 1. Using multivariable logistic regression, we will test for associations between bright light exposure and decreases in circadian misalignment and increases in circadian amplitude. The estimated association will inform the effect size in the design of future interventional studies.

SUBJECT POPULATION

Patients admitted to the Medical ICU and who meet inclusion / exclusion criteria will be recruited into this study. Decisionally impaired persons, females of childbearing potential and pregnant women who are admitted to the MICU and who meet inclusion / exclusion criteria might be recruited into this study; however, they will not be specifically recruited and subjects will be ≥ 50 years old and severe chronic brain injury is an exclusion criteria.

Table 2 (repeated)

Inclusion Criteria	Exclusion Criteria

- Hospital admission less than 30 hours as of noon on day of enrollment- Expected to stay in the MICU ≥ 24 hours after enrollment- Expected to produce ≥ 250 mL urine / day- Age ≥ 50 years- Able to understand English.	
At significant risk for pre-existing circadian abnormalities:
 
- Severe chronic brain injury (Injury greater than 30 days ago resulting in the inability to live independently) OR Acute brain injury of any severity (Injury less than 30 days ago including acute intracranial bleed, traumatic brain injury, central nervous system infection, tumor, hepatic encephalopathy)- Documented circadian disorder (<1% population) or blind/disease of the optic nerve- Current history of substance abuse including alcohol (use in last 30 days)- Transferred from an outside hospital- Homeless 
Unable to participate in study activities:
 
- History of bipolar disease (Bright light therapy possibly unsafe in this population).- Paralyzed (due to injury, disease or medications)

RECRUITMENT PROCEDURES

Patients will be screened daily from an automated list generated from the YNHH EMR. Patients who opt out of research participation via MyChart (patient information portal) will be excluded from this list.

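### Aim 3 analyses a three-arm randomised pilot by an undefined bright light exposure in a logistic model; it should compare assigned arms and report mean differences with intervals

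*Combined protocol and SAP*

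**What the plan says.** The Research Design for Aim 3 describes a randomised comparison: "Patients will be randomized via simple randomization with assignment via random number generator", to usual care (5 patients), "to bright light for 4 hours daily (n=5 patients) or to bright light for 8 hours daily (n=5 patients"). The arms sum to 15, although enrolment is given as 16; that mismatch is a separate matter.

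The Aim 3 Analytical Approach under Statistical Considerations gives one sentence on the circadian effect. With a multivariable logistic regression, "we will test for associations between bright light exposure and decreases in circadian misalignment and increases in circadian amplitude". It defines neither the exposure variable nor the binary outcome that a logistic model needs. It names no contrast among the three arms and asks for no confidence interval. There is no as-randomised statement, no analysis population, and no rule for patients who stop or miss light.

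The Aim 3 text uses the key term in two senses:
- **Light received.** If eye symptoms or headache occur, "patients will not continue bright light exposure". A patient can stop light but cannot stop an assignment.
- **The intervention.** Under Expected Outcomes: "We expect that bright light exposure is feasible, will decrease circadian misalignment, and will increase circadian amplitude".

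On the purpose of the estimate, the Rationale for Aim 3 says: "We will use this Aim to calculate effect size for use in the anticipated large-scale circadian intervention to follow this pilot RCT".

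**The concern.** A randomised trial protects its comparison only if patients are analysed in the arm they were assigned to. Here one analyst could enter assigned arm and another could enter light received. Both would be following the plan, and they could report different effects from the same patients. Stopping and missing light happen after randomisation and may be related to how ill, and so how misaligned, a patient is. An analysis by light received is then an observational one.

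The second difficulty is the model. Under Aim 1, misalignment is measured in minutes and amplitude in ng per hour, and both are analysed by linear regression as continuous outcomes. An odds ratio for an undefined decrease is neither a difference in minutes or ng/h nor an SD, and a future trial on these outcomes needs those quantities.

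This is the project's only randomised comparison, and its stated product is that effect size.

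**Working it through.** Aim 3 has no power calculation, assumed effect, alpha or stopping rate, so there is no planned figure to reproduce. Four checks follow.

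**1. The mechanism by hand (a deliberately extreme case, no true effect).** Assume that one fifth of every arm differs by 95 minutes (1 SD) in misalignment, and that exactly these patients receive no light when assigned it. Measure misalignment from the level of the other patients.
- By assigned arm (10 v 5): light (2 × 95)/10 = 19; usual care 95/5 = 19; difference 0.
- By light received (8 v 7): exposed 0; unexposed (2 × 95 + 95)/7 = 285/7 = 40.7. If the non-receivers are more misaligned, the difference is -41 minutes, an apparent benefit. If they are 95 minutes less misaligned, it is +41, an apparent harm.

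**2. Simulation under no true effect.** There were 20,000 trials per scenario, with 5 usual-care and 10 light patients. Misalignment had mean 180 and SD 95 minutes (from the Aim 1 power calculation), and the test was a two-sided 0.05 t-test. Three inputs are assumptions, not in the documents: 10% or 30% of light patients stop; the log odds of stopping per SD of severity is -1, 0, +1 or +2; and severity and misalignment correlate at 0.3 or 0.6. The model is linear and unadjusted, not the planned logistic one. Stoppers count as unexposed. Each cell gives the results for correlations 0.3 / 0.6.

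| Stopping | Log odds per SD | Bias by light received (min) | False benefit |
|---|---|---|---|
| 10% | -1 (less sick stop) | +6 / +12 | 1.9% / 1.4% |
| 10% | 0 | 0 / 0 | 2.6% / 2.3% |
| 10% | +1 | -5 / -12 | 3.1% / 4.1% |
| 10% | +2 (sicker stop) | -10 / -18 | 4.0% / 5.4% |
| 30% | -1 | +13 / +26 | 1.3% / 0.7% |
| 30% | 0 | 0 / 0 | 2.4% / 2.6% |
| 30% | +1 | -13 / -26 | 4.2% / 6.9% |
| 30% | +2 | -19 / -40 | 5.6% / 11.3% |

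Analysed by assigned arm, the mean difference was between -0.8 and +0.6 minutes in every scenario, with false benefit of 2.3% to 2.7% against a nominal 2.5%.

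**3. Logistic model.** With 15 patients the smaller outcome group holds at most 7. Three arms already use two parameters before any covariate. If all five patients in an arm fall in the same outcome group, the ordinary estimate for that arm is not finite.

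**4. Precision by assigned arm.** The half-width is t × SD × √(1/n₁ + 1/n₂), with 15 - 3 = 12 degrees of freedom and t = 2.179.
- Misalignment, 10 v 5: 2.179 × 95 × √(1/10 + 1/5) = 113 minutes.
- Misalignment, 5 v 5: 2.179 × 95 × √(2/5) = 131 minutes.
- Amplitude (Aim 1 SD 180 ng): 2.179 × 180 × √0.3 = 215 and 2.179 × 180 × √0.4 = 248.

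If the true effect were 60 minutes (an assumption), the standard error is 95 × √0.3 = 52.0. The central 90% of pilot estimates would then span 60 ± 1.645 × 52.0, or about -26 to 146 minutes.

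**The case against.** The strongest reply is that the plan never says it will set the assigned arm aside. The sentence quoted from Expected Outcomes uses the same term for the intervention, in nearly the same construction as the analysis sentence. The aim itself is framed as the effect of daytime light in a randomised pilot. Delivery of light has its own measures (tolerance, fidelity and sustainability). On this reading the sentence simply means the randomised groups.

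That reply stands against a stronger reading that a reader might infer: that the plan prescribes an as-treated analysis, moves patients who stop light to the unexposed side, and so manufactures a benefit. The documents do not support this. No section reclassifies anyone, and patients who stop for symptoms have already had some light. The direction of bias is also open. Patients able to report eye strain or headache may be the less sick, which would count against light; light missed through instability would count in its favour.

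The reply does not remove the ambiguity. In the Aim 1 models, exposure means measured light ("with light dose ratio serving as the exposure"), and room light is also recorded in Aim 3, so the light-received analysis would be easy to run. Nor does it answer the point about the logistic model, which holds under either reading.

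It is also fair to say that the precision figures describe the by-arm analysis and would remain after the change. They bear on how the estimate is used, not on the exposure question.

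**Conclusion.** The concern holds as a gap in specification plus an unsuitable model. The exposure term is undefined, and one of its two readings forfeits randomisation. The possible bias is about -40 to +26 minutes under the assumed stopping patterns, and about 0 if stopping is unrelated to severity; by assigned arm it is about 0 throughout. These figures rest on assumed stopping rates and correlations, on Aim 1's SD, and on a linear unadjusted comparison. They show possible size and sign, not a prediction.

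The logistic model does not deliver the effect size that Aim 3 seeks for continuous outcomes. Even the right comparison will be imprecise: ±113 minutes is more than one SD (113/95 = 1.19). A reader might infer that the pilot's point value alone will set the next trial's size. The text says only that the estimate will inform it, so what is needed is a statement of how.

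The plan should be changed, but this is not fatal: the trial is a small pilot whose first hypothesis is feasibility.

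**What to change.** In the Aim 3 Analytical Approach:
- State that circadian outcomes are compared by assigned arm, including every randomised patient with aMT6s data whether or not light was stopped or missed. Say how patients who leave the ICU before the end of study day 2, and so do not remain in the study, are accounted for.
- Replace the logistic test with mean differences in misalignment (minutes) and amplitude (ng/h), each with a 95% confidence interval.
- Prespecify one main contrast, for example pooled light versus usual care, with any other comparison among the 0, 4 and 8 hour arms secondary.
- Keep hours of light received as an analysis labelled exploratory.
- State that the pilot's SD and interval, not its point estimate alone, will inform the size of the next trial.

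The cost is wording and minor analysis changes. No new data are needed, and the feasibility metrics are unaffected. The by-arm estimate measures the effect of assigning light, so missed light will dilute it; the exploratory analysis keeps the information on hours received.

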Hypothesis 3.2: Daytime bright light will be associated with decreased circadian misalignment and increased circadian amplitude (effect size).

BACKGROUND:

Overall Premise: This research project addresses intensive care unit (ICU) delirium which is a significant, modifiable source of ICU morbidity and mortality. Delirium affects 50-80% of patients admitted to the medical ICU (MICU).¹ Delirium is a syndrome of acute cerebral dysfunction with features of a change in baseline mental status, inattention and either disorganized thinking or an altered level of consciousness.² Patient risk factors for ICU delirium include older age, hypertension, dementia, alcohol abuse, and chronic benzodiazepine use.² Critical illness related risk factors for delirium include severity of illness, mechanical and non-invasive ventilation, and high doses of benzodiazepines during ICU admission.^{2, 3} ICU delirium is associated with adverse outcomes such as longer hospital stay, impaired cognition, and increased mortality.⁴⁻¹¹ Additional days of delirium incrementally increase the risk of death and cognitive impairment at one year.^{3, 4} Evidence for the use of any medications to treat delirium is limited. Non-pharmacologic treatments such as sleep promotion have shown promise and are recommended by expert guidelines.^{12, 13} Currently sleep promotion efforts are focused on minimizing overnight sound, light, and care to provide patients with a sleep opportunity.¹⁴ However, there is a lack of attention to the potentially significant contribution of circadian abnormalities to the problem of ICU sleep disruption and consequent delirium.

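### Aim 3 plans multivariable logistic regression in 15–16 patients for two continuous outcomes and carries the estimate forward as the next trial's effect size; even a simple mean difference would be too imprecise for that use

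*Combined protocol and SAP*

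**What the plan says.** Approach to Aims, Aim 3, Research Design: "we will screen and enroll 16 patients", allocated by "simple randomization with assignment via random number generator" to "usual care (n=5 patients) or to bright light for 4 hours daily (n=5 patients) or to bright light for 8 hours daily (n=5 patients". The listed arms sum to 15, not 16.

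Statistical Considerations, Aim 3 Analytical Approach, gives the analysis: "Using multivariable logistic regression, we will test for associations between bright light exposure and decreases in circadian misalignment and increases in circadian amplitude". The next sentence gives its use: "The estimated association will inform the effect size in the design of future interventional studies". The Aim 3 Rationale is firmer: "We will use this Aim to calculate effect size for use in the anticipated large-scale circadian intervention to follow this pilot RCT". Hypothesis 3.2 is worded as a directional claim: "Daytime bright light will be associated with decreased circadian misalignment and increased circadian amplitude (effect size".

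For Aim 3 the plan gives no covariate list, no definition of a binary outcome, no named contrast (each dose, or both doses together, against usual care), no interval, no precision target, and no other basis for the next trial's effect size. The Aim 1 Analytical Approach, by contrast, defines misalignment in minutes and amplitude in ng per hour and models both as continuous.

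**The concern.** There are two linked problems.

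First, the model does not suit the outcome or the sample. Logistic regression needs a yes/no outcome. Applied here it would discard the minutes and ng that the measurement yields, and it would return an odds ratio that cannot be used directly to plan a trial on those scales. With 15–16 patients and several covariates it may have no finite solution.

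Second, correcting the model does not make the estimate a sound basis for design. With five patients per arm, a mean difference is compatible with a wide range of true effects, including none and a reversal. If such an estimate were used on its own to plan a larger trial in critically ill patients, that trial could be far too small or needlessly large.

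**Working it through.** The plan states no power or precision for Aim 3, so there is no figure to reproduce.

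**Inputs.** From the documents: 5 patients per arm (Aim 3 Research Design); SD 95 min around a mean of 180 min, SD 180 ng around a mean of 450 ng, and detectable shifts of 52–65 min (Aim 1 power calculation). Using those SDs for Aim 3 is an assumption.

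**1. Can the planned model be fitted?** Assume the Aim 1 covariates are carried over: age, gender, severity, sepsis (2 df), OSA risk, care events, and day and night temperature make 9 df. Two arm terms and an intercept bring the total to p = 12 parameters for n = 15. If the binary outcome is a coin toss unrelated to the covariates, Cover's counting formula gives the chance that it is perfectly separated, in which case no finite estimate exists: P(Binomial(n − 1, ½) ≤ p − 1).

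- 9 covariate df (p = 12): 1 − (91 + 14 + 1)/16384 = 0.994.
- 5 covariates (p = 8): P(Binomial(14, ½) ≤ 7) = 0.60.

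Simulation with the arm terms included agrees: about 99% and about 60%. A linear model with the same 12 parameters could be fitted, but on 3 residual df. Even with the standard error unchanged at 60.1 min (step 2), its half-width would be 3.182 × 60.1 = 191 min.

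**2. Precision of an unadjusted mean difference.** Half-width = t(0.975, df) × SD × √(1/n₁ + 1/n₂).

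| Contrast | SE | t | Half-width |
|---|---|---|---|
| 5 v 5, minutes | 95 × √0.4 = 60.1 | 2.306 (8 df) | 139 |
| 5 v 5, ng | 180 × √0.4 = 113.8 | 2.306 | 263 |
| 10 v 5, minutes | 95 × √0.3 = 52.0 | 2.160 (13 df) | 112 |
| 10 v 5, ng | 180 × √0.3 = 98.6 | 2.160 | 213 |

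For 5 v 5, an SD of 60 gives 88 min and an SD of 130 gives 190 min. Against 52–65 min, the 5 v 5 half-width is 2.1 to 2.7 times as large and the 10 v 5 half-width 1.7 to 2.2 times. A two-sided 5% t test at 5 v 5 has 12%–16% power for 52–65 min.

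Exact balance is also unlikely. Simple randomisation of 15 patients gives 5/5/5 with probability 756756/3¹⁵ = 5%.

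**3. What if a two-arm trial were sized on the estimate?** Suppose that trial uses the same endpoint, targets 90% power and takes the SD as 95. Its true power falls below 80% when the estimate exceeds the true effect by a factor of (1.960 + 1.282)/(1.960 + 0.842) = 1.157. With SE 60.1 (5 v 5):

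| True effect | Estimate ≤ 0 | Estimate > 1.157 × truth | Either |
|---|---|---|---|
| 52 min | Φ(−0.865) = 19% | 1 − Φ(0.136) = 45% | 64% |
| 65 min | Φ(−1.082) = 14% | 1 − Φ(0.170) = 43% | 57% |
| 90 min | Φ(−1.498) = 7% | 1 − Φ(0.235) = 41% | 47% |

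If the next trial also takes its SD from the pilot, simulation gives 65%, 59% and 49%. For both light arms together against usual care, the figures at 52 and 65 min are 60% and 54%.

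**A caution on the benchmark.** The 52–65 min is a shift per increment of an Aim 1 explanatory variable, not a bright-light effect. A two-group formula with the plan's inputs gives 61.6–77.0 min at 90% power; the stated range fits about 78% power. Against 61.6–77.0 min the 5 v 5 half-width is still 1.8 to 2.3 times as large, so the comparison stands.

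**The case against.** The strongest reply is that this is a pilot. Feasibility has its own criteria (70% on each metric), the analytical section says only that the estimate will inform later work, and nobody expects precision from 15 patients. This stands as a defence of the sample size, which is not criticised here. It does not defend the model, and the Rationale does name calculation of an effect size for the larger trial as a purpose of the Aim.

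A second reply is that the SD is borrowed and that repeated cycles could help. If 95 min is the SD of a single cycle and three cycles are averaged, the half-width is multiplied by √((1 + 2ρ)/3). For an assumed within-patient correlation of 0.3 to 0.7 this gives about 101 to 124 min, which is better but still wide.

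Four stronger readings are tempting and are not supported:

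- That ±139 min is the interval of the planned analysis. It belongs to an unadjusted mean difference; the logistic model yields no interval in minutes.
- That the estimate will usually mislead. This depends on the true effect and on what counts as failure. At 90 min the combined rate in step 3 is about half or less. If failure means a non-positive estimate or true power under 50%, the rate is about 45% at a true effect of 60 min.
- That a chance null could end the programme. The only threshold in the Aim 3 analysis concerns feasibility; nothing stops on the effect estimate.
- That the next trial will be the two-arm circadian trial of step 3. The Background's significance statement describes a large-scale entrainment intervention for delirium, and no sizing rule is given. Step 3 is an illustration.

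**Conclusion.** The point holds. The planned logistic model is the wrong tool for two continuous outcomes and is likely not to be estimable with more than a few covariates; the 12-parameter count assumes the Aim 1 adjustment set, which Aim 3 does not state. Replacing it with a mean difference cures the model but not the imprecision: with the Aim 1 SDs assumed to apply, no unadjusted two-arm or pooled contrast above does better than about ±112 min or ±213 ng. An estimate that loose should not set the next trial's effect size by itself. This should be changed before analysis. The feasibility objective is unaffected.

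**What to change.** 1. **Aim 3 Analytical Approach:** replace the multivariable logistic regression and its test with unadjusted mean differences by randomised arm in misalignment (minutes) and amplitude (ng per hour), using one summary value per patient. Report each light dose and pooled light against usual care, with 95% CIs and the SD.
2. **Aim 3 Rationale and Analytical Approach:** state that the pilot estimate will not by itself set the next trial's effect size. That size should rest on a prespecified important difference, with the SD taken from the pilot together with the 100-patient cohort and the feasibility rates from the pilot. The documents give no important difference, so the investigators must supply and justify one.
3. **Hypothesis 3.2:** reword it as estimation of the difference with its interval.
4. **Research Design:** reconcile the total of 16 with three arms of 5.

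No patients, samples or procedures are added. The cost is that the pilot gives up a test of efficacy it cannot support, and that the investigators must agree an important difference before the larger trial is designed. Aim 3 runs first, so the cohort SD becomes available only once Aims 1 and 2 have reported.
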